## Data analysis (annual follow up 2-5 years)

The primary outcome, time to first conviction, will be described by a Kaplan-Meier graph and summarised by the proportion with convictions by 60 months. Cox regression adjusting for pre-specified key predictors will estimate treatment effects. Secondary outcomes up to 48 months post-randomisation will be analysed by linear or logistic regression as appropriate. We will also use random effects models to explore differences between randomised groups in trajectories over time. Data on service use collected using the CA-SUS will be supplemented by a critical pathway analytic approach mapping participants' journey from initial referral to experience of adult services

The primary economic evaluation will explore cost-effectiveness in terms of the primary outcome. A cost-utility analysis will also be undertaken, using QALYs calculated using the EQ-5D (EuroQol) measure of health related quality of life (Brooks.,1996)). Analyses will be undertaken from a societal perspective. Cost-effectiveness will be explored initially by calculating incremental cost effectiveness ratios (ICERs) –difference in mean costs divided by difference in mean effects (Van Hout.,1994). Repeat re-sampling from the costs and effectiveness data will then be used to generate a distribution of mean costs and effects for the two treatments, which can be used to calculate the probability that each of the treatments is the optimal choice, subject to a range of possible maximum values (ceiling ratio) that a decision-maker might be willing to pay for a unit improvement in outcome. Cost-effectiveness acceptability curves will be presented by plotting these probabilities for a range of possible values of the ceiling ratio Fenwick et al., 2001).

The qualitative interviews will all be transcribed before undergoing a synthesis of IPA and framework analysis ([name]., 2009; Ritchie., 1994) as successfully employed in [name]'s previous

funded health research. This enables analysis to begin with a closely focused and psychological examination of the first set of transcripts using IPA. This then feeds into a framework analysis of subsequent transcripts as the balance shifts from an inductive to a more deductive phase and accommodates a large amount of qualitative data. This hermeneutic circle of analysis is completed by a final micro analysis of selected subset of cases illuminated by the complete corpus analysis.

At the end of phase 1 of the qualitative analysis, the results will be available in a series of matrices defined by variable, participant and theme which can then be examined alongside the results of the quantitative analysis of secondary outcomes. This process will take the form of a mutual interrogation and illumination. The primary output from this will be an integrated empirical paper combining quantitative and qualitative analysis. The qualitative arm will then be completed with the production of a detailed, interpretative narrative.

As well as interviewing young people and primary caregivers on their views of change or the absence of change in key outcome domains, we will explore their experiences of services and of the transition between child and adult services. We will complement the interview data from young people and caregivers around their experiences of services with semi-structured interviews of MST and MAU staff around barriers to service implementation. The interviews with staff will be conducted using a semi-structured interview based on the domains of CYPRESS, a service characterisation instrument that we have designed and validated, which will enable us to describe service configurations associated with particularly good outcomes both in the MAU and MST arms of the trial and increase the accuracy of cost estimates for the programme. The interviews will be with senior staff and case managers and the data will be analysed thematically in the same manner as the narratives collected from the semi-structured qualitative interviews with young people and caregivers.

A mixed methods approach (Creswell., 2010)) to integrate the qualitative interview data with the primary and secondary outcome measures to expand our understanding of the relationship between the variables set out above and (a) participants' and families' experience of the problems, (b) the impact of any skills acquired on participants' abilities to cope with these problems and (c) their relationship to access to services and participants' ability to engage. This will contribute to the refinement of interventions and inform the design and delivery of future services.

While a quantitative score will be obtained for each MST and MAU service based on TAMS and outcomes statistics, we will analyse interview transcripts using IPA in order to capture the rich thematic data (on service characteristics, team operations, interventions and sustainability) that is obtained from clinicians when using the semi-structured interview based on the CYPRESS Measure.

**Data Monitoring and Ethics Committee (DMEC):** An independent DMEC is being established to review the safety and ethics of the trial and will meet prior to the start of recruitment and annually thereafter. Detailed unblinded reports will be prepared by the statistician for the DMEC to monitor safety data, recruitment and drop-out rates. The formal statistical interim analysis of the primary endpoint will be reported to the DMEC after at least half the required number of events has occurred.

Scheduling: See Roadmap document below.

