#### Two to Five years post randomisation;

**Primary Aim:** The primary outcome is criminal conviction as registered on the Police National Computer.

**Secondary Aim:** Secondary outcomes will include (a) antisocial behaviour as indicated by arrest, cautions, self-report, (b) emotional well-being, including the presence or absence of psychiatric problems, (c) education and training outcomes, (d) social network, specifically the quality of relationships with parents and peers (e) self-efficacy (f) physical health, together with (g) work adjustment and (h) early (unplanned) pregnancy or fatherhood. The use of services and associated costs will be monitored. We will estimate the total social, health, educational and criminal justice cost of interventions at 48 months post-randomisation, when we will also identify the key cost and outcome drivers and value for money of the treatments.

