#### **Measures:**

Follow-up assessments will be at 6, 12, 18, 24, 36 and 48 months post randomisation, with primary outcomes collected until 5 years post randomisation.

(a) Principles of measurement: The measures will be made across multiple domains (specific to criminal behaviour, family function, user satisfaction, comorbid problems and economic costs), using multiple methods (interviews, questionnaires, records), and multiple sources (adolescent, parent, teachers) to maximise the clinical validity of the outcome assessments and minimise bias arising from any single source of information. Where possible, measures will be made by individuals blind to treatment allocation. Many of the measures have been selected because they are part of an ambitious project under-way in the Parenting Academy (Scott, Dabbs et al.) with a range of samples, including with a large sample of looked after children, which will provide UK norms against which the current sample may be compared.

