
There may be further concerns attached to using out of home placement as a primary outcome. It is possible to envision a situation whereby the presence of the MST team would influence the likelihood of court or other systems deciding to place the young person away from the family. It is also possible that the presence of the MST team, affording a more accurate view of family function, may precipitate the placement of the young person outside the home. These types of influences which suggest that the primary outcome measure may be 'reactive' with the planned intervention would compromise randomisation, and compromise the trial. In order to minimise these problems we have placed the endpoint of the study at 18 months in order to see if the impact of MST may be felt over the course of the year that follows the intervention. It is unlikely that over this period the measure (long-term placement out of home) would be reactive with the intervention.

The other domains we consider key to the intervention are (a) forensic outcomes, (b) adolescent wellbeing outcomes and (c) family functioning outcomes. In addition of course, in line with the research brief, we consider the economic data collected alongside these outcomes to be key.

*Key Forensic Outcome:* We have considered a range of forensic outcomes related to the antisocial behaviors which remain a key part of the definition of the target population. Perhaps the most meaningful key forensic outcome would be reconviction rates which over a short term follow-up based on 3 studies favours MST compared to standard care with an RR of .51, (95%CI .23, 1.16). The likelihood of reconviction during the course of treatment is 30% and over 18 months from randomisation is about 50% based on a combination of US and Canadian studies. We will use time to offences (categorised as per annual statistical reports Youth Justice Board, 2007) that resulted in a pre-court disposal (Reprimand or Final Warning) or a court disposal. Access to this information will have been approved by the YJB. In collaboration with the YJB, we will also examine whether MST reduces use of custodial sentences and hence service costs.

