#### Design and Methodology (Annual follow up from 2-5 years)

The annual follow-up period from 2 years post randomisation will extend the primary outcome window to 60 months and carry out an evaluation of a broadened range of outcomes of both MST and MAU to 48 months. We will conduct annual full-blind outcome evaluations up to 48 months post-randomisation. Data on service use will be collected using the Child and Adolescent Service Use Schedule (CA-SUS) and Children & Young People, Resources, Evaluation and Systems Schedule (CYPRESS) (Pilling et al., 2012). Data will be used to characterise services and provide currently lacking information on transitions from child to adult services, identifying correlates of a smooth transition (continuation of appropriate services across the 18-year barrier) and testing the hypothesis that transition is important to relatively better outcomes. A a semi-structured interview will explore young people's and primary caregivers' views of change or the absence of change in key outcome domains and the families experiences of services and of the transition between services.

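### The 2-5 year economic evaluation has no single horizon (costs at 48 months, conviction outcome at 60), and the conviction endpoint as worded does not exclude offences committed before randomisation

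*Protocol*

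**What the plan says.** **Clinical outcome.** In the protocol's aims for two to five years after randomisation, "The primary outcome is criminal conviction as registered on the Police National Computer". The matching data analysis section adds the time scale: "The primary outcome, time to first conviction, will be described by a Kaplan-Meier graph and summarised by the proportion with convictions by 60 months". The 60-month window is repeated elsewhere. Measures lists assessments up to 48 months, "with primary outcomes collected until 5 years post randomisation". The design section for the annual follow-up has this wording: "extend the primary outcome window to 60 months and carry out an evaluation of a broadened range of outcomes of both MST and MAU to" (the sentence then names month 48 as the limit for those broader outcomes).

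**Costs.** The same aims paragraph says: "We will estimate the total social, health, educational and criminal justice cost of interventions at 48 months post-randomisation". Its next clause places the value-for-money assessment at that time too. Service use is recorded with the CA-SUS at interview (Measures, economic evaluation), and the annual outcome evaluations run to 48 months.

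**Economic analysis.** The 2-5 year data analysis section says: "The primary economic evaluation will explore cost-effectiveness in terms of the primary outcome". It defines the ICER as the difference in mean costs over the difference in mean effects and names no horizon for either.

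**Event date.** The 18-month forensic outcome (Measures, Key Forensic Outcome) is dated by offence: "We will use time to offences (categorised as per annual statistical reports Youth Justice Board, 2007) that resulted in a pre-court disposal" or a court disposal. The 2-5 year primary outcome is described only as time to first conviction. No rule is given for convictions that relate to offences before randomisation.

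**The concern.** **Horizon.** An ICER is interpretable only if costs and effects cover the same period. As written, a conviction in month 55 would enter the effect while the service costs around it would not. The cost-effectiveness acceptability curves, built by resampling the same costs and effects, would inherit the mismatch.

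**Event definition.** A young person may be convicted after entry for an offence committed before it. MST cannot prevent that offence. In a time-to-first-event analysis such a conviction counts as an event and also takes the place of any later offending by that person. Carried-over cases are plausible here: one of the alternative suitability criteria requires recent convictions, the forensic route asks for them or for a supervision order, and the Accrual section speaks of a triggering offence behind referrals. The cost would be a diluted treatment effect and lost power on the long-term primary outcome.

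**Working it through.** **Plan's own figures.** The protocol states no power or expected rate for the 2-5 year conviction endpoint. Its only power figures concern out-of-home placement at 18 months: 30% against 20%, 350 per arm, 86%, falling to 83% with a design effect of 1.22 in the MST arm. A two-sided 5% test (alpha assumed, as it is not stated) with the normal approximation gives 86.5% and, with 350/1.22 = 287 effective MST participants, 82.6%. Both reproduce, and neither is affected by this point. They serve only to check the power formula used below.

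**Horizon gap.** Effects to 60 months less costs to 48 months leaves 12 months.

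**Effect on the ICER.** The same cost difference appears in both ratios and cancels:

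ICER with 60-month effect / ICER with 48-month effect = D48 / D60,

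where D is the absolute difference in the proportion convicted. With constant hazards, 18-month control rate p and hazard ratio 0.75:

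D(T) = (1 − p)^(0.75·T/18) − (1 − p)^(T/18).

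Inputs: p = 50% is the reconviction rate over 18 months in the Key Forensic Outcome paragraph, taken from US and Canadian studies. The lower values of p are assumptions. The hazard ratio of 0.75 is also an assumption. (Table 1 gives 0.75, 95% CI 0.52 to 1.07, for incarceration or conviction at 1.7 years.)

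Worked for p = 50%:
- 48 months: 0.5^2 − 0.5^2.667 = 0.2500 − 0.1575 = 0.0925
- 60 months: 0.5^2.5 − 0.5^3.333 = 0.1768 − 0.0992 = 0.0776
- Ratio: 0.0925 / 0.0776 = 1.19

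| 18-month control rate | D48 | D60 | ICER ratio |
|---|---|---|---|
| 10% | 0.0549 | 0.0646 | 0.85 |
| 20% | 0.0885 | 0.0971 | 0.91 |
| 30% | 0.1037 | 0.1054 | 0.98 |
| 50% | 0.0925 | 0.0776 | 1.19 |

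At low rates the curves are still separating at 48 months. At high rates most of both arms have been convicted and the curves are converging. The ratio therefore crosses 1.

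**Dilution by earlier offences.** Let a share q of each arm be convicted after randomisation for an earlier offence, unrelated to their later risk. Let later offences lead to conviction in 50% (control) and 37.5% (MST) of the others, so that the risk ratio is 0.75. The observed proportion in each arm is q + (1 − q) × rate. For q = 10%:
- control: 0.10 + 0.90 × 0.50 = 0.550
- MST: 0.10 + 0.90 × 0.375 = 0.4375
- risk ratio: 0.4375 / 0.550 = 0.795

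Power is for a comparison of proportions with 350 per arm, two-sided 5%, without the therapist design effect:

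| q (assumed) | Control | MST | Difference | Risk ratio | Power |
|---|---|---|---|---|---|
| 0% | 0.500 | 0.375 | 0.125 | 0.75 | 91.7% |
| 5% | 0.525 | 0.406 | 0.119 | 0.77 | 88.5% |
| 10% | 0.550 | 0.438 | 0.113 | 0.80 | 84.7% |
| 20% | 0.600 | 0.500 | 0.100 | 0.83 | 75.9% |
| 30% | 0.650 | 0.562 | 0.087 | 0.87 | 65.9% |

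The documents give no value for q.

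**The case against.** **On the horizon.** The aims put costs and value for money at the same time, 48 months. Setting the evaluation in terms of the primary outcome can be read as naming the measure (conviction) and not its cut-off, and a time-to-event outcome can be read off at 48 months. This stands as far as it goes: a reader might infer that the ICER is wrong by construction, and the documents do not support that. They allow a 48-month evaluation on both sides but do not prescribe one, and the analysis section that defines the primary outcome gives only 60 months.

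**On earlier offences.** A reader might infer that the protocol decides to count them. It does not say so. The wording leaves them in because no limit is set, and a dating rule may sit in an analysis plan that is not at hand. The 18-month outcome belongs to another phase and does not spell out an exclusion either. Still, dating by offence with the clock at randomisation removes earlier offences, and dating by conviction does not. The later phase departs from the earlier practice without giving a reason.

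**On who is recruited.** It would be too strong to say that the sample is selected for recent offending. Only one of the five alternative suitability criteria requires convictions, and the generic risk features accept a mere risk of offending. The recent-conviction rule belongs to the forensic route and concerns cases already dealt with, not pending ones.

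**On bias.** A reader might also infer bias between arms. Allocation is 1:1, with minimisation that includes number of past convictions, so carried-over events should be balanced in expectation. They attenuate the effect and favour neither arm.

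**Conclusion.** The concern holds in two limited parts.

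First, the 2-5 year economic evaluation has two unreconciled horizons, 12 months apart. Taken literally, the ICER would be about 0.85 to 1.19 times its 48-month value. That range rests on constant hazards, an assumed hazard ratio of 0.75 and assumed 18-month control rates of 10% to 50%. Quoting only the 19% increase would mislead: it is one end of the range, tied to a reconviction rate from North American studies, and the sign reverses at lower rates.

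Second, the long-term primary event is worded so that convictions for offences before randomisation are not excluded. The consequence is dilution and lost power. At an assumed 10% affected and rates of 50% against 37.5%, the risk ratio moves from 0.75 to 0.80 and power from about 92% to 85%. The true share cannot be obtained from the documents, so the size is illustrative. It also assumes that carried-over cases are unrelated to later offending.

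Both should be settled before the long-term analysis, because better rules are available at little cost.

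**What to change.** 1. State one horizon for the 2-5 year economic evaluation: conviction by 48 months as the effect, matching the costs (and the QALYs, provided the EQ-5D follows the same assessment schedule). Keep 60 months for the clinical primary outcome. Extending costs instead would need service-use collection that the protocol does not schedule.

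2. Define the 2-5 year primary event as the first offence committed after randomisation that leads to a conviction recorded on the Police National Computer. Date it by the offence, start the clock at randomisation for all randomised participants, and do not count convictions for earlier offences.

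**Cost.** The first change is wording only. The second needs an offence-date field in the records extract and a stated lag, so that offences near the cut-off have time to reach conviction. Without that lag, late offences would be under-counted.

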# Figure 2: Anticipated screening and consenting procedure and attrition rates

# **START** Systemic Therapy for At Risk Teens: Roadmap

egin:	Trial Year 1	Mar	Trial Year 2	Mar	Trial Year 3	Mar	Trial Year 4	Tr
lar 2009 Rec	cruitment Target 200	Phased 2010	Recruitment Target 450	2011	Recruitment Target 50	2012		Compl
	Staggered	outcomes		1		12 Month	18 month	Mar 20
Consultation	recruitment	assessment		Recru	itment Treatment &	Outcomes	Outcomes	
and set-up	begins	l begins		col	nplete 6-month Outcomes	complete	Complete	
phase	Jun 2009	Dec 2009		Ma	2011 complete Nov 2011	May 2012	November 2012	
group • Dev	Month 3-6	report forms and ran Recruit and train RAs	ation forms • Pilot client rec domisation systems • Participation in MST train MG and DMEC • Database	ing and settir	ng up of MST supervisors' g			-
Ongoing ree	Month 4-27 cruitment - geograpi	hically staggered ea	rly start sites at each Centre	• Administra	tion of pre-treatment measu	res • Randomisation		
Treatment -	Month 4-33 – duration of 3-6 mo	onths for families ran	domised to MST					
	Month						athlesses to final states	- 11 12
Collect treat	tment characteristic	; Information - 3 mon	ths post randomisation • Co	liect Econom	ic Data - 3 months post rand	domisation and 3 mol	nthiy up to final data c	collection
		Month 10-33						
	d secondary outcom	ie assessment at 6 r	nonths post randomisation -	minimum of	2 weeks after family comple	te MST		
Primary and			Month 16-39					
Primary and			MONULI 10-39					
	d secondary outcom	ie assessment at 12	months post randomisation	l				
Primary and			months post randomisation Month 22-	45				
Primary and			months post randomisation Month 22- months post randomisation	45				
Primary and			months post randomisation Month 22-	45				

 
Primary and
 
Primary and
 
	d secondary outcom	ne assessment at 18	months post randomisation Month 22- months post randomisation	45 45				

